14.2 Clinical Trial Site Monitoring

Clinical site monitoring is conducted to ensure that the rights and well-being of trial subjects are protected, that the reported trial data are accurate, complete, and verifiable, and that the conduct of the trial is in compliance with the currently approved protocol/amendment(s), with International Conference on Harmonisation Good Clinical Practice (ICH GCP, and with applicable regulatory requirement(s).

- Monitoring for this study will be performed by the Sponsor or designee

- Details of clinical site monitoring are documented in a Clinical Monitoring Plan (CMP). The CMP describes in detail who will conduct the monitoring, at what frequency monitoring will be done, at what level of detail monitoring will be performed, and the distribution of monitoring reports.
- If needed, independent audits will be conducted to ensure monitoring practices are performed consistently across all participating sites and that monitors are following the CMP.

14.3 Audit and Inspection

The trial site also may be subject to quality assurance audits by the Sponsor or designees.

For the purpose of ensuring compliance with the clinical study protocol, GCP and applicable regulatory requirements, the Investigator should permit auditing by or on behalf of the Sponsor and inspection by regulatory authorities.

The investigational site will provide direct access to all trial related sites, source data/documents, and reports for the purpose of monitoring and auditing by the Sponsor, and inspection by local and regulatory authorities.

The Investigator will make every effort to help with the performance of the audits and inspections, giving access to all necessary facilities, data, and documents.

As soon as the Investigator is notified of a planned inspection by the authorities, he/she will inform the Sponsor and authorize the Sponsor to participate in this inspection.

The confidentiality of the data verified, and the protection of the subjects should be respected during these inspections.

Any result and information arising from the inspections by the regulatory authorities will be immediately communicated by the Investigator to the Sponsor.

The Investigator shall take appropriate measures required by the Sponsor to take corrective actions for all problems found during the audit or inspections.

14.4 Responsibility of Investigator

The Investigator is required to ensure compliance with all procedures required by the clinical trial protocol and with all trial procedures provided by the Sponsor (including security rules).

The Investigator agrees to provide reliable data and all information requested by the clinical trial protocol (with the help of the CRF, discrepancy resolution form, or other appropriate instrument) in an accurate and legible manner according to the instructions provided and to ensure direct access to source documents to the Sponsor representatives.

If any circuit includes transfer of data, particular attention should be paid to the confidentiality of the subject's data to be transferred. The Investigator may appoint such other individuals as he/she may deem appropriate as Sub-investigators to assist in the conduct of the clinical study in accordance with the clinical trial protocol.

All Sub-investigators shall be appointed and listed in a timely manner. The Sub-investigators will be supervised by and work under the responsibility of the Investigator. The Investigator will provide them with a copy of the clinical trial protocol and all necessary information.

To providing written summaries of the status of the study to the IRB/IEC annually or more frequently in accordance with the requirements, policies, and procedures established by the IRB/IEC.

To notifying the IRB/IEC of SAEs or other significant safety findings as required by IRB/IEC procedures.

Signed copy of Investigator's undertaking should be provided as an appendix.

14.5 Responsibility of Sponsor

The Sponsor of this clinical trial is responsible to regulatory authorities for taking all reasonable steps to ensure the proper conduct of the clinical study as regards ethics, clinical study protocol compliance, and integrity and validity of the data recorded on the CRFs. Thus, the main duty of the monitoring team is to help the Investigator and the Sponsor maintain a high level of ethical, scientific, technical, and regulatory quality in all aspects of the clinical study.

At regular intervals during the clinical study, the site will be contacted, through monitoring visits, letters, or electronically, by a representative of the monitoring team to review study progress, Investigator and subject compliance with clinical study protocol requirements, and any emergent problems.

These monitoring visits will include but not be limited to review of the following aspects: subject's informed consent, subject recruitment and follow-up, SAE documentation and reporting, AE documentation, IP allocation, IP accountability, concomitant therapy use, and quality of data.

14.6 Protocol Deviation

A protocol deviation is any noncompliance with the clinical trial protocol, ICH GCP, or Manual of Procedures (MOP) requirements. The noncompliance may be either on the part of the subject, the Investigator, or the study site staff. As a result of deviations, corrective actions are to be developed by the site and implemented promptly. Details can be found in the study specific Protocol Deviation Plan or the Clinical Monitoring Plan.

15. PUBLICATION AND DATA SHARING POLICY

The Sponsor will comply with the requirements for publication of study results. In accordance with standard editorial and ethical practice, the Sponsor will generally support publication of multicenter studies only in their entirety and not as individual site data. In this case, a coordinating investigator will be designated by mutual agreement. Requests for publication of site-specific data should be presented to the Sponsor for review and approval at least 90 days prior to submission for publication.

Appendix 1: Clinical Laboratory Tests

- The tests detailed in [Table 9](#) will be performed by the local laboratory, unless otherwise specified.
- Protocol-specific requirements for inclusion or exclusion of subject are detailed in [Section 5](#).
- Additional tests may be performed at any time during the study as determined necessary by the Investigator or required by local regulations.
- Investigators must document their review of each laboratory safety report.

Table 9 Protocol-Required Laboratory Assessments

Urine drug screen	amphetamines, methamphetamines, methadone, barbiturates, benzodiazepines, cocaine, opiates, methylenedioxymethamphetamine, phencyclidine, tetrahydrocannabinol
Other laboratory assessments	Hepatitis B surface antigen, hepatitis C virus antibody, and human immunodeficiency virus antibody types 1 and 2 (Screening only) Female subjects serum pregnancy tests at screening Female subjects Point-of-Care urine pregnancy tests prior to dosing at Day 1 Alcohol test at screening and prior to dosing on Day 1

Appendix 2: Country-specific Requirements

Not applicable.

Appendix 3: Adverse Events Grading

Grading of Solicited Adverse Events

Subjects should be instructed to rate Solicited Symptoms of Reactogenicity that are collected within their Solicited Symptom Diary based on the severity scale presented in [Table 10](#).

Table 10 Grading of Solicited Symptoms of Reactogenicity

Symptom	Grading				
	Normal 0	Mild Grade 1	Moderate Grade 2	Severe Grade 3	Life Threatening Grade 4
Fever (oral temp)	< 100.4°F (< 38.0°C)	100.4 – 101.1°F (38.0 – 38.4°C)	101.2 – 102.0°F (38.5 – 38.9°C)	102.1 – 104°F (39.0 – 40°C)	> 104.0°F (>40°C)
Headache	None	No interference with activity	Repeated use of nonnarcotic pain reliever > 24 hours or some interference with activity	Significant; any use of narcotic pain reliever or prevents daily activity	ER visit or hospitalization
Myalgia (muscle pain)	None	AE easily tolerated, causing minimal discomfort and does not interfere with everyday activities ^a	Adverse event sufficiently discomforting to interfere with everyday activities	Adverse event prevents normal everyday activities or requires medical advice	ER visit or hospitalization
Abdominal Pain	None	No interference with activity	Some interference with activity not requiring medical intervention	Prevents daily activity and requires medical intervention	ER visit or hospitalization
Anorexia	None	No interference with activity	Some interference with activity not requiring medical intervention	Prevents daily activity and requires medical intervention	ER visit or hospitalization
Nausea	None	No interference with activity or 1 to 2 episodes	Some interference with activity or >2 episodes	Prevents daily activity, requires outpatient IV hydration	ER visit or hospitalization for hypotensive shock
Vomiting	None	No interference with activity or 24 hours	Some interference with activity or 24 hours	Prevents daily activity, requires outpatient IV hydration	ER visit or hospitalization for hypotensive shock
Diarrhea	None	2 to 3 loose stools or < 400 gms/24 hours	4–5 stools or 400 to 800 gms/24 hours	6 or more watery stools or > 800gms/24 hours or requires outpatient IV hydration	ER visit or hospitalization
Malaise/ Fatigue	None	No interference with activity	Some interference with activity	Significant; prevents daily activity	ER visit or hospitalization

^a Everyday activity include attendance at work, school, and usual habits of the subjects.**Appendix 4: Contraceptive Guidance and Collection of Pregnancy Information****Definitions***Postmenopausal female:*

- A postmenopausal state is defined as no menses for 12 months without an alternative medical cause.

Contraceptive Guidance

- Contraceptive use by women should be consistent with local regulations regarding the use of contraceptive methods for those participating in clinical studies. Subjects must be willing to use a highly effective form of contraception for 30 days prior to vaccination and until 60 days after the vaccination. Acceptable forms are oral, implantable, intrauterine, transdermal, intravaginal, injectable, double barrier or abstinence (subjects using diaphragms must also use condom). A reliable form of contraception must be approved by the Investigator.
- While abstinence is allowed, periodic abstinence (e.g., calendar, ovulation, symptothermal, post-ovulation methods) and withdrawal are not acceptable methods of contraception.
- A negative pregnancy test will be required for all female subjects prior to study drug administration, as outlined in the SoA ([Table 1](#)).

Collection of Pregnancy Information

Female subjects who become pregnant:

- The investigator will attempt to collect pregnancy information on any female subjects.

After obtaining the necessary signed ICF from the pregnant female subject, the investigator will record pregnancy information on the appropriate form and submit it to the Sponsor within 24 hours of learning of the pregnancy. The Sponsor will attempt to follow the female subject to determine the outcome of the pregnancy. Information on the status of the mother and child will be forwarded to the Sponsor. The Sponsor will follow the female subject until birth or termination of pregnancy when possible. Any termination of the pregnancy will be reported regardless of fetal status (presence or absence of anomalies) or indication for the procedure.

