3.2. End Points

3.2.1. Primary End Points

- **Safety**
 - Frequency, duration, and severity of solicited symptoms of reactogenicity (local, systemic) for 1 week following each dose of study drug
 - Frequency, duration, and severity of unsolicited treatment-emergent adverse events (TEAEs), serious AEs (SAEs), adverse events of special interest (AESIs), and new onset of chronic illness (NOCIs) through the active period (4 weeks post last dose).
- **Immunogenicity**
 - Serum VP1 specific (GI.1 and GII.4) IgA through the active period measured by Meso Scale Discovery (MSD) assay by dose level
 - Geometric mean concentration (GMC) at Day 1, Day 8 and Day 29
 - Geometric mean fold rise (GMFR) from Day 1 to Day 8 and from Day 1 to Day 29
 - Breastmilk VPI specific (GI.1 and GII.4) IgA through the active period measured by Meso Scale Discovery (MSD) assay by dose level
 - Geometric mean concentration (GMC) at Day 1, Day 8, and Day 29
 - Geometric mean fold rise (GMFR) from Day 1 to Day 8 and from Day 1 to Day 29

- The number of subjects in each dose group that had a 2-fold GMC rise or greater in breast milk VP1 specific IgA (GI.1 and GII.4) between Day 1 and any other timepoint.

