Adverse Event of Special Interest (AESIs)

An adverse event of special interest (serious or nonserious) is one of scientific and medical concern specific to the Sponsor's product or program, for which ongoing monitoring and rapid communication by the Investigator to the Sponsor can be appropriate. For this study, AESIs are serious or non-serious adverse events of scientific and medical concern with potential immune-mediated medical conditions as well as events associated with thrombosis and thrombocytopenia as listed in but not limited to [Table 11](#).

New Onset of Chronic Illness (NOCIs)

New Onset of Chronic Illness is defined as diagnosis post-enrollment and vaccination of a new medical condition, which is chronic in nature, including those potentially controllable by medication (e.g., diabetes, asthma).

Adverse Reaction

All noxious and unintended responses to an investigational product related to any dose should be considered adverse reactions (AR). (The phrase "responses to an investigational product" means that a causal relationship between a medicinal product and an AE is at least a reasonable possibility.)

Additional Sponsor Definition

a. Solicited Adverse Events-

- i. Solicited adverse events (AEs) are predefined signs and symptoms of reactogenicity for which the subject is specifically questioned, and which are noted by the subject in their Solicited Symptom Diary, including:

- fever (any temperature 100°F or higher)
- headache
- myalgia (muscle pain)
- abdominal pain
- anorexia (defined and not eating)
- nausea
- vomiting
- diarrhea
- malaise/fatigue

- ii. Subjects will utilize a Solicited Symptom Diary issued on the day of the vaccination to record solicited any TEAE daily for the one week following that administration.

b. Unsolicited Adverse Events

- i. An unsolicited AE is an observed AE that does not fulfill the conditions prelisted in the eCRF in terms of diagnosis and/or onset window post-vaccination; this also includes progression of chronic diseases. Unsolicited AEs includes both serious (SAEs) and non-serious unsolicited AE.

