14. QUALITY CONTROL AND QUALITY ASSURANCE

14.1 Early Safety Data Review AND/OR Committee

Subject safety will be continuously monitored by the Sponsor or designee, which includes safety signal detection during the study.

All safety data collected will be summarized and reviewed by the sponsor's internal/external safety monitoring committee for agreement of next steps.

In particular, data will be reviewed by the sponsor for identification of the following events that would potentially contribute to a requirement to [pause/stop] the study.

- One or more subjects experiences a treatment-related serious adverse event (SAE) of any grade
- Two or more subjects experience the same treatment-related grade ≥ 3 solicited symptom within one week following vaccination.
- Two or more subjects experience the same treatment-related unsolicited grade "severe" AE between Day 1 and Day 29 (Active Period).

Enrollment will be paused during the review. If a pausing/stopping rule is met, a decision will be made, based on the review, as to whether enrollment in the study will be allowed to resume. If no dose-related toxicities are observed, and upon the recommendation of the SMC following review of safety data, enrollment of the remaining subjects will be initiated.

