#### 13.1 Solicited Symptoms of Reactogenicity

Solicited symptoms are predefined signs and symptoms of reactogenicity for which the subject is specifically questioned, and which are noted by the subject in their Solicited Symptom Diary, including:

- Fever (any temperature 100.4°F or higher)
- Headache
- Myalgia (muscle pain)
- Abdominal Pain
- Anorexia (defined and not eating)
- Nausea
- Vomiting
- Diarrhoea
- Malaise/Fatigue

Subjects will utilize a Solicited Symptom Diary issued on the day of the vaccination to record solicited symptom daily for one week (from Day 1 to Day 8) following that administration. After Day 8 solicited symptoms will be captured as unsolicited Adverse Events as described in [section 13.2](#) with Day 8 as date of onset.

The count and percentage of subjects and the associated Clopper-Pearson 95% CIs reporting at least one solicited symptom during 8 days after vaccine administration (the 8 days include Day 1) will be summarized for each dose and presented by severity and cumulatively across severity levels as listed below:

- Grade 1 Solicited Symptoms
- Grade 2 Solicited Symptoms
- Grade 3 Solicited Symptoms
- Grade 4 Solicited Symptoms

where Grade 1 is mild, Grade 2 is moderate, Grade 3 is Severe, and Grade 4 is Potentially Life threatening as defined in Table 10 “Grading of Solicited Symptoms of Reactogenicity”.

Missing reactogenicity Diary data will not be imputed.

All the solicited symptoms collected during the active period of the study will also be presented for each treatment arm, study day, by severity in by-subject listing.

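### Table 10 leaves some abdominal pain and anorexia reports without a grade and others with two possible grades, so the severity results and the Grade 3 count behind the pause rule are not fully defined

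*Protocol*

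**What the plan says.** Protocol (version 2.0) Section 3.2.1 makes this a primary safety endpoint: "Frequency, duration, and severity of solicited symptoms of reactogenicity (local, systemic) for 1 week following each dose of study drug". The mother grades first. Appendix 3 states "Subjects should be instructed to rate Solicited Symptoms of Reactogenicity" on the Table 10 scale.

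The relevant cells of Table 10 are:

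- **Abdominal pain and anorexia.** Grade 2 needs some interference and no medical intervention. Grade 3 is "Prevents daily activity and requires medical intervention".
- **Myalgia.** Grade 3 is "Adverse event prevents normal everyday activities or requires medical advice", so either condition is enough. Headache Grade 3 also uses *or*, and malaise Grade 3 needs only that daily activity is prevented.
- **Nausea and vomiting.** Grade 3 lists prevented activity and outpatient IV hydration, separated by a comma.
- **Vomiting, Grade 2.** As extracted, this reads "Some interference with activity or 24 hours", and Grade 1 carries the same 24-hour phrase.

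SAP 13.1 tabulates solicited symptoms by grade, and cumulatively, with Clopper-Pearson 95% intervals, and takes the grades from Table 10. Protocol 7.1.2 asks a qualified person to review the diary. The only marks it says must be checked against Table 10 are those already at Grade 3. One trigger in Protocol 14.1 is "Two or more subjects experience the same treatment-related grade ≥ 3 solicited symptom within one week following vaccination".

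On fever, Protocol 9.1 has "fever (any temperature 100°F or higher", Table 10 grades anything below 100.4°F as normal, and SAP 13.1 has "Fever (any temperature 100.4°F or higher".

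**The concern.** A grading scale that feeds a primary endpoint should send every report to exactly one grade. Here a woman kept in bed by cramps who receives no treatment is too ill for Grade 2 and fails the second half of Grade 3. If she or the site marks Grade 3, the check in 7.1.2 would remove that mark, because the table requires intervention as well, and there is no Grade 2 for the event to fall into. If she marks something lower, no specific check is asked for. The same incapacity from fatigue, headache or muscle pain is Grade 3.

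Neither document says what to do with a report that fits no grade or two grades. SAP 13.1 does not impute missing diary data, and SAP 3.1 calculates percentages on non-missing data, so an ungraded entry could drop out of the severity table. The vaccine is designed to act in the ileum (Protocol 6.1), so the gastrointestinal rows are a natural place for a dose-related signal to appear. The pause rule counts Grade 3 or higher events and takes on whatever the table leaves open.

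**Working it through.** The plan gives no expected Grade 3 rate, power or precision figure on this point (SAP 3.3 plans no hypothesis testing), so there is nothing to reproduce. The check takes each row literally, crosses its own criteria and lists the grades each combination meets.

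**1. Abdominal pain and anorexia** (emergency visit or hospitalisation, Grade 4, left aside):

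| Activity | Medical intervention | Grade met |
|---|---|---|
| no interference | no | 1 |
| no interference | yes | 1 |
| some interference | no | 2 |
| some interference | yes | none |
| prevented | no | none |
| prevented | yes | 3 |

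Two of 6 combinations have no grade.

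**2. Nausea** (3 activity levels × 2 episode levels × IV hydration no/yes = 12). If the Grade 3 comma means *and*, 6 of 12 combinations meet two grades. If it means *or*, 10 of 12 meet two or more. Nausea that prevents activity without IV hydration is Grade 1 (1 to 2 episodes) or Grade 2 (more than 2) under *and*, but also meets Grade 3 under *or*.

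**3. Diarrhoea** (5 stool categories × 3 weight bands, no IV hydration = 15). Six of 15 meet two grades. For example, six or more watery stools weighing under 400 g in total meet Grades 1 and 3.

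**4. Fever.** 100°F = (100 − 32) × 5/9 = 37.8°C, and 100.4°F = 38.0°C. The passages conflict only for 100.0 to 100.3°F. Table 10 starts Grade 3 at 102.1°F, so this conflict cannot change a Grade 3 count.

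**5. Effect on a severity percentage.** Arms are 30, 30 and 16 (Protocol 11.1). One regraded woman moves a vaccine arm by 1/30 = 3.3 points and placebo by 1/16 = 6.3 points. Exact intervals are:

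- 2/30 = 6.7%, 95% CI 0.8% to 22.1%
- 0/30 = 0%, 95% CI 0% to 11.6% (upper limit 1 − 0.025^(1/30) = 0.116)

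**6. Effect on the pause count.** The documents give no rate, so p is an assumption: the chance that a vaccinee has one given related symptom that prevents activity without medical intervention. With 60 vaccinees, P(at least 2) = 1 − (1 − p)^60 − 60p(1 − p)^59.

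| Assumed p | P(at least 2) if counted as Grade 3 | If not counted |
|---|---|---|
| 1% | 12% | 0 |
| 2% | 34% | 0 |
| 3% | 54% | 0 |
| 5% | 81% | 0 |

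The last column means no contribution from these women; events that meet the full Grade 3 wording still count.

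**The case against.** The best defence is that the trial is randomised, double-blind and descriptive, so loose grading has no stated reason to favour an arm. Qualified staff review the diary, ideally daily, and Protocol 8 has women with severe events contact the site for evaluation. The triggers in 14.1 only potentially contribute to a pause. The Medical Monitor can ask for a Safety Monitoring Committee review, the committee may also meet on trends, and its charter, which is not among these documents, governs.

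Much of this stands. An incapacitated participant is not invisible to oversight, and no bias between arms is shown. But the results are percentages per arm and the pause trigger is an absolute count. Both can be too low even when the error is equal across arms, and the review relies on the same incomplete table.

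Five stronger readings are tempting, and the documents do not support them:

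- **The fever conflict disturbs the fever analysis or the pause rule.** SAP 13.1 uses one threshold, which matches Table 10, and the conflict lies well below Grade 3. Section 9.1 is out of line on what is recorded as fever.
- **A woman dosed at 37.8 to 37.9°C counts as a fever case with no rise.** Protocol Table 7 treats solicited symptoms as treatment-emergent, which requires onset or worsening after dosing, and she is below the SAP threshold.
- **The frequency of solicited symptoms is undefined.** Most defects move a symptom between grades and leave the any-grade count alone. The exceptions are the fever line, a single loose stool judged by stool count alone, and ungraded entries if they are dropped.
- **The roughly 7 sites will grade differently.** That is possible, but nothing in the documents shows it.
- **Vomiting Grades 1 and 2 share a criterion.** The repeated 24-hour phrase may be characters lost when the PDF was read, so it carries no weight here.

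**Conclusion.** The concern holds for severity. Abdominal pain and anorexia each leave 2 of 6 combinations ungraded, the nausea and vomiting Grade 3 cells are undecided between *and* and *or*, and the nausea and diarrhoea rows overlap with no tie-break. The severity part of the primary reactogenicity endpoint and the Grade 3 or higher pause count can therefore be under-counted or inconsistent. The 2/30 to 0/30 change is an illustration that needs both women to fall in the gap and be graded down; it is not a forecast. The pause-rule probabilities rest on assumed rates of 1% to 5%. The fever mismatch is a separate contradiction confined to recording at 100.0 to 100.3°F. This is worth correcting before unblinding, but it does not undermine the trial as a whole.

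**What to change.** Before the Day 29 unblinding (Protocol 4.4), the sponsor's safety group should:

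1. Reconcile the Table 10 rows so that every combination of a row's own criteria maps to exactly one grade.
2. State *and* or *or* in the nausea and vomiting Grade 3 cells.
3. State a tie-break for reports that meet two grades. The diarrhoea row needs it too, so that row cannot serve as the model. A tie-break alone will not close the gaps in abdominal pain and anorexia.
4. Check the vomiting row against the source document.
5. Reconcile the fever passages in Protocol 9.1, Table 10 and SAP 13.1.
6. Confirm how the pause rule in 14.1 reads against the corrected table.

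Which grade or temperature limit is right is for that group to decide. The SAP should carry the resulting derivation rule, including how a report that fits no grade is shown, and list it in Section 15.

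For diaries already collected, blinded staff should flag affected entries. They should re-grade only if the diary holds the components (activity, intervention, episodes). The documents do not show that it does; the planned diary listing (16.2.7.2) mentions only the severity grade.

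The cost is protocol and diary wording plus a short derivation note. Amendment 1 already reworded the neighbouring pause trigger because unsolicited events have no numerical grade (Protocol Appendix 6), so this is the same kind of correction. The downside is that some events may change grade.
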